9.5 Additional Secondary Analyses

All secondary analyses in this section will be performed on both the FAS and PP populations. Treatment failures will be imputed as baseline for continuous endpoints, and will be imputed as the worst outcome for categorical outcomes (e.g. non-responder).

Missing data due to dropouts will not be imputed for these secondary analyses.

9.5.1 Percentage of Articular Defect Fill according to MRI at 12 and 24 months

The number and percentage of subjects with Articular Defect Fill according to MRI will be summarized by arm and visit (12 and 24 months). The percentages between arms will be compared at each visit with a two-sided Chi Square test with significance alpha = 0.05.

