# X-ray may be performed lying down or standing, per patient comfort

\* Screening MRI and X-ray must not be older than 1 year

\*\* MRI and Defect Fill evaluation is performed at 12 and 24 months. Additionally, MRI will be performed at 3 and 6 months to an initial cohort of at least 25 patients per study groups to evaluate presence of cysts

A Post Approval Multicenter Open-label

Randomized Controlled Trial of Agili-C™ vs.

Surgical Standard of Care (SSOC) for the  
Treatment of Joint Surface Lesions of the Knee

CLN0021-US

Rev. 8

March 29, 2022

\*\*\* MRI and X-ray will be performed according to PI decision

\*\*\*\* According to PI decision if surgery is performed. The biopsy will be sent to a central lab.

^ The 3 month visit may take place ±2 weeks

^ The 6 month visit may take place ±12 weeks

∞ Not applicable for the 3 months visit

“ Optional MRI

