### **Assessment Personnel**

The MRI images will be assessed in a blinded fashion off-site. Two certified radiologists experienced in MRI evaluation of cartilage repair will assess each imaging study independently. The degree of cartilage defect volume fill will be semi-quantitatively assessed by each radiologist separately in increments of 25% fill on a scale grade of 1-5 (i.e 0-24% fill [1], 25-49% fill [2], 50-74% fill [3], 75%-99% fill [4], and 100% fill [5]). When the radiologist's averaged scores differ by up to two grades, the two scores are averaged. When the radiologist's scores differ by two or more grades, a third blinded radiologist will assess the specific imaging study and then the three scores will be averaged.

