### **Assessment Score**

On each MRI scan, 2-3 slices located within the implant/lesion on a sagittal scan and 2-3 slices located within the implant/lesion on a coronal scan will be assessed by each examiner. To enable for accurate assessment, the radiologists will be provided an information regarding the number, size and location of the lesions. Each slice will be scored in 25% increments (Figure 6). Results of these slices will be averaged. Thus, each score is a composite average of 4-6 slices in both sagittal and coronal orientation. In certain notch lesions and trochlear lesions axial cuts allow better evaluation of the defect and thus will be used. In addition to average defect fill, minimum and maximum defect fill scores will be recorded (Figure 6).

A Post Approval Multicenter Open-label

Randomized Controlled Trial of Agili-C™ vs.

Surgical Standard of Care (SSOC) for the  
Treatment of Joint Surface Lesions of the Knee

CLN0021-US

Rev. 8

March 29, 2022

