4.3 Secondary Efficacy Endpoints

Secondary endpoints will include:

- Percentage of Articular Defect Fill according to MRI at 12 and 24 months
- Change from baseline in average overall KOOS score (Pain, Symptoms, QOL, ADL & Sports) at 6, 12, and 18 Months
- Change from baseline in IKDC Subjective Knee Evaluation at 12, 18, and 24 Months
- Change from baseline in Tegner score at 12, 18, and 24 Months
- Change from baseline QOL as measured by SF-12 v2 at 6, 12, 18, and 24 Months
- Change from baseline to 24 months in the average overall KOOS score (Pain, Symptoms, QOL, ADL & Sports) in patients with chondral lesions
- Change from baseline to 24 months in the average overall KOOS score (Pain, Symptoms, QOL, ADL & Sports) in patients with osteochondral lesions
- Change from baseline to 24 months in the average overall KOOS score (Pain, Symptoms,

QOL, ADL & Sports) in patients with single lesion

- Change from baseline to 24 months in the average overall KOOS score (Pain, Symptoms, QOL, ADL & Sports) in patients with multiple lesions
- Change from baseline to 24 months in the average overall KOOS score (Pain, Symptoms, QOL, ADL & Sports) in patients without osteoarthritis (K/L 0-1)
- Change from baseline to 24 months in the average overall KOOS score (Pain, Symptoms, QOL, ADL & Sports) in patients with osteoarthritis (K/L 2-3)
- Change from baseline to 24 months in the average overall KOOS score (Pain, Symptoms, QOL, ADL & Sports) in patients with total lesion(s) size $\leq 3\text{cm}^2$
- Change from baseline to 24 months in the average overall KOOS score (Pain, Symptoms, QOL, ADL & Sports) in patients with total lesion(s) size $> 3\text{cm}^2$
- Change from baseline to 24 months in the average overall KOOS score (Pain, Symptoms, QOL, ADL & Sports) in patients with previous ligament reconstruction
- Change from baseline to 24 months in the average overall KOOS score (Pain, Symptoms, QOL, ADL & Sports) in patients without previous ligament reconstruction
- Change from baseline to 24 months in the average overall KOOS score (Pain, Symptoms, QOL, ADL & Sports) in patients with intact meniscus
- Change from baseline to 24 months in the average overall KOOS score (Pain, Symptoms, QOL, ADL & Sports) in patients with previous partial meniscectomy
- Change from baseline to 24 months in the average overall KOOS score (Pain, Symptoms, QOL, ADL & Sports) in patients with concomitant partial meniscectomy

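### SAP 9.5.1 tests the percentage of subjects with defect fill by chi-square, but fill is scored as an averaged 1-5 grade and no supplied text says which grades count.

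*SAP*

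**What the plan says.** SAP 4.3 lists the endpoint as "Percentage of Articular Defect Fill according to MRI at 12 and 24 months", which describes how much of the defect is filled. SAP 9.5.1 keeps that title but changes the quantity: "The number and percentage of subjects with Articular Defect Fill according to MRI will be summarized by arm and visit". The test follows: "The percentages between arms will be compared at each visit with a two-sided Chi Square test with significance alpha = 0.05".

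The SAP does not define the measure. Protocol Appendix 2 does. Fill is "semi-quantitatively assessed by each radiologist separately in increments of 25% fill on a scale grade of 1-5", and the lowest grade covers 0-24%. For each reader, "each score is a composite average of 4-6 slices in both sagittal and coronal orientation". Scores are then averaged over two readers, or three after adjudication, and over all of a patient's lesions. The fill immediately after the procedure is set to zero in both arms.

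Two rules bear on treatment failures. SAP 9.5 gives failures the baseline value for a continuous endpoint and the worst outcome for a categorical one. SAP 10.4 says additional secondary data are not imputed at all.

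**The concern.** A test of proportions needs a rule that sorts each subject into one of two groups. For KOOS response the SAP supplies one, a gain of at least 30 points (SAP 4.2), and sets out the model (SAP 9.4). For defect fill it supplies none. The grading scale cannot stand in for it, because an unfilled lesion and a 20% filled lesion both receive grade 1.

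Two analysts could therefore produce different p-values from the same reads. A cut-off chosen after the reads were seen would let that choice affect the result. The failure rule is open for the same reason, since 9.5.1 does not say whether the endpoint is continuous or categorical.

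**Working it through.** The documents give no effect size, SD, event rate or power for defect fill, so there is no figure of the plan's own to reproduce. The check takes each reading of SAP 9.5.1 in turn.

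**Reading 1: every graded subject counts as having fill.** The smallest possible grade is 1, so both arms are at 100%. The pooled proportion is p = 1, p(1 - p) = 0, and the statistic is 0/0. The alternative, any fill above 0%, cannot be recovered because grade 1 includes 0%.

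**Reading 2: a single cut-off on the averaged score.** For a normal score cut so that a fraction p lies above it, the information kept relative to comparing means is φ(z_p)² / [p(1 - p)]:

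| Cut | Calculation | Kept | Lost |
|---|---|---|---|
| median | 0.3989² / 0.25 | 64% | 36% |
| 25/75 | 0.3178² / 0.1875 | 54% | 46% |
| 10/90 | 0.1755² / 0.09 | 34% | 66% |
| 5/95 | 0.1031² / 0.0475 | 22% | 78% |

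The median is the best case. More than half is lost only when the cut lies outside about the 21st to 79th percentile.

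In power terms, assume a 0.4 SD shift, normality, a two-sided 0.05 test, and 160 versus 79 subjects. The counts are the KOOS FAS numbers in protocol 10.7.1, not counts of MRI reads.

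- Means: the SE in SD units is √(1/160 + 1/79) = 0.1375, and 0.4/0.1375 = 2.909. Power from the noncentral t is 82.6%.
- Wilcoxon: 2.909 × √(3/π) = 2.843, and Φ(2.843 - 1.960) = 81%.
- Chi-square at the control median: the proportions are 0.500 and Φ(0.4) = 0.655, a difference of 0.155. The SE is 0.0672 under the null and 0.0676 under the alternative. Power is Φ[(0.1554 - 1.960 × 0.0672)/0.0676] = Φ(0.349) = 64%.

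| Cut at control percentile | 2 | 10 | 25 | 50 | 75 | 90 |
|---|---|---|---|---|---|---|
| Chi-square power | 18% | 37% | 54% | 64% | 59% | 42% |

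Over all cuts the maximum is about 64%, so the unstated cut-off alone moves power between 18% and 64%.

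**Reading 3: a 2×5 chi-square across grades.** This needs no cut-off, but the patient score is an average: two readers at 3 and 4 give 3.5. No rounding rule is given, and the test ignores the order of the grades. A simulation used a latent fill SD of 25 points, slice noise SD of 15, two readers and five slices, the same arm sizes, a shift of about 10.4 points and 2,000 runs. With control mean fill of 40% and 60%, power was 55% and 60% for the 2×5 test, 81% and 82% for Wilcoxon, and 82% and 84% for the t-test. Between 87% and 89% of averaged scores were non-integer. All of these inputs are assumptions.

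**The case against.** The strongest reply is that reading 3 is natural. The Appendix 2 form offers five boxes, and SAP 9.2 summarises categorical endpoints by count and percentage. On that reading the test is neither empty nor dependent on a cut-off. This stands in part: the reading is workable once a rounding rule is added, but the SAP does not state it, and the wording about subjects with fill does not describe it.

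Several stronger claims that a reader might infer are not supported:

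- *The test throws away most of the information.* This is true only for extreme cuts; a median cut keeps about 64%.
- *Nearly every subject has some fill.* The documents give no fill distribution, and grade 1 includes 0%. That every scored subject has a grade does not show that every subject has fill.
- *The open-label design biases the measurement.* Appendix 2 has the images read off-site and blinded, with a third blinded reader for disagreements. What is exposed is the analyst's choice of cut-off, not the reading.
- *The 60-month result is affected.* Protocol Table 2 keeps the reads ("MRI and Defect Fill evaluation is performed at 12 and 24 months"), but marks none at 36 to 60 months, and defect fill is not in the protocol's endpoint lists.

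It is also fair to say that the issue may be retrospective. Protocol 10.7.1 already reports Month 24 KOOS results, and protocol 10.5 cites a September 2021 analysis report. Choosing a new test now has the same weakness as choosing a cut-off late. Finally, the grading scale comes from the 2022 post-approval protocol. The pivotal protocol is not supplied, so the claim can only be that the supplied documents contain no definition.

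**Conclusion.** The concern holds in a limited form. The test in SAP 9.5.1 does not match the variable that Appendix 2 produces, and it cannot be run from the supplied text without a decision that the text does not record. Under normality any single cut-off costs at least about 36% of the information. The gap between 81-83% power on the averaged score and at most about 64% after a cut is illustrative: it rests on the assumed 0.4 SD shift, on normality, and on KOOS counts used in place of MRI counts. Failures placed at the bottom of the scale would depart from normality, so these figures show the direction and rough size only.

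The consequence is modest. Defect fill is an additional secondary endpoint of the 24-month analysis, outside the confirmatory hierarchy, and cannot decide trial success.

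**What to change.** In SAP 9.5.1, compare the subject-level averaged defect-fill grade between arms at 12 and 24 months with a Wilcoxon rank-sum test. Report an estimate with a 95% interval, for example the probability that an Agili-C subject has a higher grade than an SSOC subject. Give the distribution over the Appendix 2 grades as description only.

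State the treatment-failure rule for this endpoint and reconcile it with SAP 10.4. One option consistent with SAP 9.5 is to give failures the lowest rank. A rank test is then little affected by whether the imputed value is the post-procedure zero or grade 1, since both fall at the bottom.

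If the 24-month analysis has been run, disclose the cut-off or grouping used and when it was chosen. Report the averaged-grade comparison beside it, labelled post hoc. A cut-off shown to have been fixed before the reads, with its rounding and failure rules, would settle the definition but keep the loss of power.

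The cost is a few sentences and a re-run on existing reads, with no new imaging. Two drawbacks remain: a rank comparison is less simple to quote than a percentage, and a test specified now carries less weight than one fixed beforehand.

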9.5.2 Analysis of Secondary Endpoints over time

The following endpoints will be analyzed by 1) providing descriptive statistics by arm and visit, 2) graphically summarize the endpoint by treatment arm at each visit using box plots to visually inspect the time trend, and 3) performing a repeated measures analysis using a mixed effects model with terms for treatment, visit, and treatment-by-visit interaction. In the model we will use the values recorded at each visit, including the baseline visit.

The test for the treatment by visit interaction will be considered significant if the p-value is less than 0.05. No adjustments will be made for multiplicity, and results will be interpreted with caution due to the multiple tests.

The following secondary efficacy endpoints will be analyzed in this way:

- Change from baseline in average overall KOOS score (Pain, Symptoms, QOL, ADL & Sports) at 6, 12, and 18 Months
- Change from baseline in IKDC Subjective Knee Evaluation at 12, 18, and 24 Months
- Change from baseline in Tegner score at 12, 18, and 24 Months
- Change from baseline QOL as measured by SF-12 v2 at 6, 12, 18, and 24 Months

9.5.3 Subgroup Analyses on the Primary Endpoint

The primary endpoint (change from baseline to 24 months in the average overall KOOS score (Pain, Symptoms, QOL, ADL & Sports) will be analyzed in the following subgroups:

- Lesion type (chondral or osteochondral)
- Number of lesions (single or multiple)
- Level of osteoarthritis (K/L score 0-1 or 2-3)
- Lesion size (total lesion size $\leq 3\text{cm}^2$ or $> 3\text{cm}^2$)
- Previous ligament reconstruction (with or without)
- Meniscus status (intact, previous partial meniscectomy, concomitant meniscectomy)
- Activity status (active or inactive)

For each of the categories above, summary statistics will be provided for the primary endpoint by arm and subgroup. Within each subgroup, the means of the two treatment arms will be compared using a Bayesian analysis similar to that for the Primary analysis; however, no imputation of dropouts will be performed.

9.6 Safety Analyses

Safety analyses will be conducted on the safety analysis set and will include all AEs, SAEs and USADEs.

The following summaries will be provided:

- An overall summary of the number and percentage of patients and AEs by SOC (System Organ Class) and PT (Preferred Term).
- An overall summary of the number and percentage of patients and events of SAEs by SOC and PT
- An overall summary of the number and percentage of patients and events of USAEDs by SOC and PT
- An overall summary of the number and percentage of patients and events of AEs by SOC, PT and Severity.
- An overall summary of the number and percentage of patients and events of AEs by SOC, PT and Outcome.

Anticipated AEs, listed in the eCRF, will be described by their pre-specified terms as collected in the eCRF. AEs which are not pre-specified in the eCRF will be coded and aggregated using MedDRA (Medical Dictionary for Regulatory Activities) version 18.2.

The AEs will be summarized with frequency and percentage of total subjects and number of events, and will be summarized and presented by treatment group.

For the summaries of AEs, subjects who experience the same AE more than once will only be counted once for that event in the number of subjects, but all occurrences of the same event will be counted in the number of events.

The AEs related to the implant, the tool-set and the procedure will be summarized with frequency and percentage of total subjects and number of events by these categories and by their pre-specified terms as collected in the eCRF, when applicable.

9.6.1 *Treatment Failure Rate*

The Treatment Failure Rate will be summarized with the number and percentage of subjects experienced Treatment Failures (section 5.0). The percentages between arms will be compared with a two-sided Chi Square test with significance alpha = 0.05

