**A Post Approval Multicenter Open-label****Randomized Controlled Trial of Agili-C™ vs.**

**Surgical Standard of Care (SSOC) for the  
Treatment of Joint Surface Lesions of the Knee**

CLN0021-US

Rev. 8

March 29, 2022

	

Follow-up will be performed at 2 weeks and at 3, 6, 12, 18 and 24 months post-procedure and yearly thereafter, until each patient reaches 60 months follow up to evaluate the patient's knee condition and clinical health

Questionnaires will be completed at baseline and at 6, 12, 18 and 24 months and yearly thereafter, until each patient reaches 60 months follow up.

Anterior-Posterior (A/P) and Lateral knee X-rays will be taken at 2 weeks and at 6, 12, 18, 24, 36, 48- and 60-months post procedure

Annual Knee MRI is optional, until each patient reaches 60 months follow up.

Knee and AE related medications will be recorded at each visit.

Patients that drop out or withdraw consent will not be replaced.

Statistical Considerations:	See Section 10.0

A Post Approval Multicenter Open-label

Randomized Controlled Trial of Agili-C™ vs.

Surgical Standard of Care (SSOC) for the  
Treatment of Joint Surface Lesions of the Knee

CLN0021-US

Rev. 8

March 29, 2022

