## 5.7 Overall Study Design

This is a post approval, multicenter, open-label, randomized, and controlled trial of Agili-C™ vs. SSOC for the repair of joint surface lesions. Candidates will be evaluated by the investigator based on an MRI and X-ray (NMT one year old), clinical history and physical examination. Prior to Screening, the candidate will sign and date the ICF. Following signing of the informed consent, subjects will undergo Initial Screening using study questionnaires. The PI will send the candidate's MRI and standing X-ray for off-site K/L assessment. In case of K/L<4 and absence of clear exclusion criteria as seen on baseline MRI, not more than 90 days after Initial Screening, subjects will undergo Final Screening via Arthroscopy. Arthroscopic findings will verify the subject's eligibility for study enrollment, and if found eligible will be enrolled into the study and randomized intra-operatively into either Agili-C™ or SSOC. Agili-C™ implantations will be performed via an arthrotomy or mini-arthrotomy procedure, using a designated surgical toolset. In SSOC, microfracture and/or debridement procedures will be performed arthroscopically according to standard practice. Follow-up will be performed at 2 weeks and at 3, 6, 12, 18- and 24-months post-procedure and yearly thereafter, until each patient reaches 60 months follow up, to evaluate the patient's knee condition and clinical health. Questionnaires will be completed at baseline and at 6, 12, 18 and 24 months and yearly thereafter until each patient reaches 60 months follow up. Anterior-Posterior (A/P) and Lateral knee X-rays will be taken at 2 weeks and at 6, 12, 18, 24, 36, 48- and 60-months post procedure. Annual Knee MRI is optional.

	CLN0021-US-Investigational Plan A Post Approval Multicenter Open-label Randomized Controlled Trial of Agili-C™ vs. Surgical Standard of Care (SSOC) for the Treatment of Joint Surface Lesions of the Knee	Document Number: CLN-0000002 Document Version: 8.0 Effective Date: 08-Jun-2022 (GMT+2) Page 20 of 80 CLN0021-US Rev. 8 March 29, 2022
--	--	---

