#### **7.3.4 Three months post procedure visit ± 2 weeks (Visit 4)**

1. Analgesic, anti-inflammatory and prescription medication recording
2. Record AEs/SAEs
3. MRI will be performed at 3 months to an initial cohort of at least 25 patients per study groups to evaluate presence of cysts

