## 9.10 Anticipated Adverse Events Related to the Implant include:

- Transient or chronic pain and/or swelling and/or effusion of the operated joint
- Bone marrow edema
- Allergic or pseudo-allergic reaction and/or elevation of acute phase reactants
- Pseudo-septic reaction
- Reactive arthritis
- Bone cyst, bone fracture, bone deformities or bone aseptic necrosis
- Implant fracture, loosening or extrusion, with or without generation of particulate debris
- Abrasion of counter or nearby tissues
- Failure to induce tissue regeneration
- Tissue hypertrophy or intra-lesional bone formation
- Wound complications:
  - superficial or deep infections
  - septicaemia
  - wound dehiscence
  - hematoma or site drainage

- Intra-articular adhesions, hypertrophic tissue, hypertrophic synovitis, intra-articular adhesion, hypertrophic synovium or host reactions
- Inflammation of the joint and surrounding tissues
- Joint locking and limited range of motion, stiffness and arthritifibrosis
- Deep Vein Thrombosis
- Infection and related symptoms
- Elevation of the subchondral bone plate
- Degeneration of the surrounding cartilage
- Lack of cartilage integration
- Delamination
- Progression of degenerative changes and osteoarthritis
- Muscle atrophy

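### After Month 24 MRI is optional but safety is analysed on all treated subjects, so rates of new MRI-dependent findings are lower bounds and their arm difference moves with scan uptake

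*SAP*

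**What the plan says.** **Imaging schedule.** The footnotes to Protocol Table 2 (7.4) say "MRI and Defect Fill evaluation is performed at 12 and 24 months". After that, the synopsis (2.0, Methods) says "Annual Knee MRI is optional, until each patient reaches 60 months follow up"; Protocol 7.3.9 and Table 2 agree. For unscheduled visits, "MRI and X-ray will be performed according to PI decision". X-rays stay mandatory: "Lateral knee X-rays will be taken at 2 weeks and at 6, 12, 18, 24, 36, 48- and 60-months post procedure" (Protocol 5.7).

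**What counts as an event.** Protocol 9.10 lists anticipated implant-related adverse events. They include "Bone marrow edema", "Bone cyst, bone fracture, bone deformities or bone aseptic necrosis", elevation of the subchondral plate, failed cartilage integration and delamination. The protocol itself treats MRI as the way to find cysts early (7.3.4): "MRI will be performed at 3 months to an initial cohort of at least 25 patients per study groups to evaluate presence of cysts".

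**Denominator.** The safety set in Protocol 10.2.1 is everyone who received either treatment, and 10.6.1 runs the safety analyses on it. Protocol 10.8 says events will be tabulated but names no percentage denominator. The only explicit wording is in SAP 9.6: "The AEs will be summarized with frequency and percentage of total subjects and number of events". That SAP is the 24-month plan: its safety endpoint (4.4) stops at 24 months, and its schedule has no MRI at the later annual visits.

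Neither document gives a denominator of scanned subjects, a count of scans by arm, or a criterion for who is offered the optional scan.

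**The concern.** If a finding can be seen only on MRI, a subject who was not scanned cannot contribute an event but still sits in an all-treated denominator. The table then cannot distinguish no finding from no scan.

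The trial is open-label, so the choice to scan can depend on the arm as well as on symptoms. A difference between arms in new late findings could therefore reflect who was scanned.

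Long-term device safety is part of the primary objective (Protocol 2.0), and Protocol 11.0 has safety results posted publicly after each interim progress report. A low late rate of marrow edema or delamination could be read as reassurance, or an imbalance as a signal, without support for either.

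**Working it through.** The plan states no adverse-event rate, MRI-finding rate or scan uptake, so there is no figure of its own to reproduce. Every incidence, uptake and detection share below is an assumption.

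**1. New findings after Month 24.** Let q be the true new incidence, s the share of affected subjects scanned while the finding is visible, and x the share of unscanned cases found another way, such as by X-ray. With no false positives, the all-treated rate is

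R = q × [s + (1 − s) × x].

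R cannot exceed q, and it equals q only if s = 1 or x = 1. For q = 10% and x = 0:

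- s = 10%, 25%, 50%, 75%, 100% gives R = 1.0%, 2.5%, 5.0%, 7.5%, 10.0%.

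**2. Equal truth, unequal uptake.** With q = 10% in both arms and x = 0:

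- Agili-C at 50%: 0.10 × 0.50 = 5.0%. SSOC at 20%: 0.10 × 0.20 = 2.0%.
- With uptake swapped: 2.0% versus 5.0%.

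For scale, take the full-analysis-set sizes in Protocol 10.7.1, 160 and 79. True new cases would be 16 and 7.9, and the table would show 16 × 0.50 = 8 and 7.9 × 0.20 = 1.6.

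**3. Findings partly visible without MRI.** If 30% of unscanned cases are found another way (x = 0.3):

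- 0.10 × (0.50 + 0.50 × 0.3) = 6.5%.
- 0.10 × (0.20 + 0.80 × 0.3) = 4.4%.

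The gap narrows from 3.0 to 2.1 points. This case is closer to cysts than to marrow edema.

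**4. Cumulative rate to 60 months.** Suppose scheduled scans have already found p = 10% by Month 24, and 10% of the rest develop a new finding:

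- True: 0.10 + 0.90 × 0.10 = 19.0%.
- Tabulated at 50% uptake: 0.10 + 0.90 × 0.10 × 0.50 = 14.5%.
- Tabulated at 20% uptake: 0.10 + 0.90 × 0.10 × 0.20 = 11.8%.

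The shortfall remains, but the ratio between arms falls from 5.0/2.0 = 2.5 to 14.5/11.8 = 1.2.

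**5. Would dividing by scanned subjects suffice?** With q = 10%, let affected knees be scanned with probability 0.6 and others with 0.2:

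- Share scanned: 0.10 × 0.6 + 0.90 × 0.2 = 24%.
- Rate per treated subject: 0.10 × 0.6 = 6%.
- Rate per scanned subject: 6/24 = 25%.

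The truth, 10%, lies between the two. If everyone is scanned with probability 0.5, the rates are 5% per treated subject and 10% per scanned subject, and the second is correct. The two rates bracket the truth when affected knees are at least as likely to be scanned as others. Neither rate is enough alone.

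**The case against.** The case against has several parts, and some of it stands.

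- **The explicit denominator is in the 24-month SAP.** This is correct. Within its own horizon, MRI is scheduled at 12 and 24 months, so SAP 9.6 is not at fault. A reader might infer that it is, but the point belongs to the 60-month protocol, where an all-treated denominator follows from 10.2.1 and 10.6.1 without being spelled out.
- **The 60-month rate includes earlier findings.** This also stands. A reader might infer that the whole 60-month rate shrinks in proportion to uptake. It does not, because scheduled scans at 12 and 24 months feed the same total (step 4).
- **The documents do not say which events need MRI.** True: 9.10 gives no mode of detection, and the adverse-event definition in 9.1 does not expressly cover silent imaging findings. The only off-site follow-up MRI reading specified is for defect fill. MRI dependence is therefore an inference. It is reasonable for marrow edema and delamination, and weaker for cysts, which the scheduled X-rays may show.
- **The consequences are limited.** Reoperation, conversion and failure rates do not depend on optional scans, and SAP 9.6 tests only treatment failure between arms. This stands, and keeps the point to one of reporting.
- **All-treated percentages are conventional.** They are, but the convention is informative only when detection is similar across subjects, and here nothing planned shows whether it was.

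**Conclusion.** The point holds for new findings after Month 24 that depend on MRI. For these, the all-treated rate in each arm is a lower bound, assuming no false positives, and the arm difference can be distorted in either direction when uptake differs. Its size cannot be known from the documents; 5% versus 2% at a common true 10% shows what assumed uptakes of 50% and 20% would do.

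Stopped follow-up adds to the shortfall. Under Protocol 7.3.9, visits end after later index-knee surgery unless medically needed, yet the subject stays in the treated set.

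A reader might infer a bias in favour of the device. The documents do not support a direction, because they say nothing about who will be scanned. Nothing here touches the primary endpoint or any stated figure.

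**What to change.** In Protocol 10.8, and in any SAP written for the 60-month analysis (not in the 24-month SAP 9.6):

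- Name in advance the adverse-event terms treated as MRI-detected, and split their tabulation at Month 24.
- For Months 36, 48 and 60, report the number scanned by arm and by scheduled or unscheduled visit. Add the reason for the scan if it is recorded; the documents do not show that it is.
- For these terms, give the rate per scanned subject beside the rate per treated subject.
- State that the all-treated rate of new findings is a lower bound, and that neither rate supports a comparison of arms when uptake differs.

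The cost is one extra safety table, with no change to visits, treatment or endpoints. The downside is that per-scanned rates can overstate when scanning follows symptoms, which is why both rates are shown.
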